## **IRB Protocol**

## **JHM IRB - eForm A – Protocol**

- Use the section headings to write the JHM IRB eForm A, inserting the appropriate material in each. If a section is not applicable, leave heading in and insert N/A.
- When submitting JHM IRB eForm A (new or revised), enter the date submitted to the field at the top of JHM IRB eForm A.

\*\*\*\*\*  
\*\*\*\*\*

### **1. Abstract**

Older African American women experience disproportionate rates of chronic conditions in comparison to other groups. Pain, depressive symptoms, and frailty often co-occur in African American women aging with chronic conditions and this combination can lead to disability and poor quality of life. Addressing pain and depressive symptoms may improve or delay the progression to frailty. To our knowledge there is little work being done in this population to address both pain and depression. The Depression and Pain Perseverance through Empowered Recovery (DAPPER) program is person directed and will consist of 8 nurse visits during which the nurse assesses each participant for pain, depression, and frailty, then implements a manualized individually tailored intervention. The data collection visits, and nurse visits will take virtually. We propose a pilot trial that is a wait list randomized control pilot to test the acceptability and obtain a preliminary effect size for the intervention. We will recruit 64 ( $\geq$ age 50) African American women who report pain intensity of 3 or higher that interferes with their activities, depressive symptoms lasting more than two weeks, are pre frail or frail, and live in the community/are not institutionalized. The sample will be recruited through the PI's previous study, community recruitment flyers distributed virtually, and word of mouth campaigns. Participants will be randomized into either the intervention or the wait list control group. Once the intervention group has completed their visits, the wait list control group will begin their visits. All participants will be offered the same information and format of nurse visits. The nurses will systematically tailor the content of the visits to the participants' risk profile and goals based on protocols. All participants will be assessed at the start of the study, at 12 weeks, and 24 weeks. The primary outcomes will be pain, depressive symptoms, and frailty status. Other endpoints include goal attainment, stress (cytokines), self-report, self-efficacy, and communication with health care providers. We will also examine the acceptability of the intervention using intervention compliance and one-on-one qualitative interviews. This study will offer either virtual or in person visits based on the preference of the participants.

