### **2. Objectives**

The aims of this pilot project are to 1) test the Depression and Pain Perseverance through Empowered Recovery (DAPPER) program for feasibility and acceptability. Specifically, we will 1) test the effect size of DAPPER on pain and depressive symptoms from baseline to 12 weeks (compare intervention to wait list control group) and then at 24 weeks to compare the intervention group to wait list control group once again, 2) estimate preliminary effect sizes for DAPPER in reduction of frailty, and 3) measure effect sizes and feasibility of measuring cytokines.

This study is being supported through funding from the Harold Amos Medical Faculty Program and the Johns Hopkins Older Adults Independence Pepper Center.

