## **DAPPER Protocol**

### **Inclusion/Exclusion Criteria**

Inclusion criteria: 1) self-reported pain  $\geq 3$  out of a 0 -10 scale that has lasted longer than 3 months and keeps them from doing at least one activity that they would like, 2) Self-Identify as African American/Black female 3) non-institutionalized and living in the community Maryland, Virginia or Washington DC area. 4) score a 5 or higher on the PHQ9 (depression measure) at least two times during a two week period (screening call and then at first data collection visit via video), 5) pre-frail ( one or two criteria on frailty phenotype) or frail (three or more of the criteria on frailty phenotype), 6) at least one ADL or IADL limitation Exclusion Criteria: 1) Hospitalized  $> 3$  times in the last year, 2) participating in physical therapy, 3) have a terminal diagnosis ( $< 1$  year expected survival), 4)  $\geq$  moderate intellectual impairment (5-7 errors) based on the Short Portable Mental Status Questionnaire (SPMSQ), 5) Unable to understand or speak English

We will recruit participants from the PI's Communication Behaviors and Development of Pain and Depression Intervention among Older African American Women (IRB000170533) study. This study consisted of focus groups for the development of the DAPPER intervention. We will only contact participants who agreed to be contacted for future studies. We will contact these participants by phone and ask them if they are interested in participating in the intervention (please see the phone script). If participants agree to this, we will screen them on the phone at this time.

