**Comorbid Conditions:** We will measure comorbid conditions with the Charlson Comorbidity Index. The Charlson comorbidity index consists of 17 categories of chronic conditions including two subcategories for diabetes and liver disease. Comorbidities are based on mortality risk and severity of the disease; the scores for each disease range from 1-6. A final Charlson Comorbidity Index score is compiled; scores greater than or equal to five indicate more chronic conditions and increased risk of mortality.

**Physical Function:** Physical function will be assessed by measuring ADLs Katz ADL and Lawton's IADL measures. On Katz's ADLs scores range from 0-6 with 6 indicating full function and a score of 2 or less indicating sever functional impairment. On Lawton's IADL instrument scores range from 0-8 and higher scores indicate better physical function.

**Frailty** will be assessed by the physical frailty phenotype (includes gait speed, grip strength, BMI, and measures of physical activity and exhaustion). The frailty phenotype is used to determine if a person is robust (score of 0), pre-frail (score of 1 or 2), or frail (score of 3-5). The Frail Scale will be used to measure frailty for virtual data collection visits. The Frail Scale asks self-report questions about fatigue, resistance, ambulation, illnesses, and loss of weight.

**Stress** will be measured by perceived stress as it often accompanies depression and/or pain. We will measure using the perceived stress scale. The scores can range from 0-40; higher scores indicate more perceived stress.

**Self-efficacy** is a large part of self-regulation. We are going to measure self-efficacy using the coping and self-efficacy scale. The scores range from 0-26 with higher scores indicating more self-efficacy.

**Readiness to change** will be used to identify participants' readiness to change. The levels include 1-pre-contemplation, 2-contemplation, 3- preparation, and 4- action and maintenance. This will allow the nurses to identify where participants are on this scale and determine if strategies or goals need to be adjusted or reevaluated based on readiness to change scores.

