##### **Analytic approach:**

For DAPPER, the outcomes will be improvement in pain, depressive symptoms, and communication with health care providers. A database will be created and stored on a password protected encrypted computer. Prior to conducting the analysis, the distribution of the data will be examined to determine if they meet the assumptions of the analytical model and to explore the pattern of missing data. The number of sessions attended will be computed as an indicator of acceptability. To test the effect of the intervention on outcomes (depressive symptoms, pain), generalized estimating equations will be used (GEE) with time, group, and the time x group interaction. We will not be sufficiently powered to detect a significant effect; interpretation of the results will be based on the effect size associated with the time by group interaction for each outcome. One advantage of GEE is it allows all participants' data to be included in the analysis, even those who do not complete the study, providing an intention-to-treat analysis. We will also conduct sensitivity analyses with completers only and compare the effect size to the ITT analysis to estimate the effect size when all participants adhere to the intervention.

Acceptability of the intervention will be examined in multiple ways. We will examine percentages of people who stayed in each arm of the study and conduct numerous descriptive correlational analyses of the

association between the intervention compliance and other variables. These analyses will quantify intervention implementation by demographic and participant health variables. Analyses that utilize the post-randomization data (e.g. treatment compliance) will be evaluated in supplementary analyses. We will distinguish non-compliance with intervention from attrition or loss to follow-up, i.e. missing data. We will also use the one-on-one qualitative interviews to examine acceptability of the intervention.

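### No scale is stated for the frailty effect size; if three-band frailty status is used, six of the nine possible one-point moves from entry scores 1 to 5 go unseen

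*Combined protocol and SAP*

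**What the plan says.** The Abstract states: "The primary outcomes will be pain, depressive symptoms, and frailty status". The Outcomes section, under Frailty, says the phenotype classifies a person as "robust (score of 0), pre-frail (score of 1 or 2), or frail (score of 3-5". It describes the phenotype as one that "includes gait speed, grip strength, BMI, and measures of physical activity and exhaustion", which is five components behind a score of 0 to 5. The inclusion criteria admit women who are "pre-frail ( one or two criteria on frailty phenotype) or frail (three or more of the criteria on frailty phenotype", so phenotype scores at entry run from 1 to 5.

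The second specific aim in the Objectives is to "estimate preliminary effect sizes for DAPPER in reduction of frailty". It names neither a scale nor a time point. The Analytic approach describes a model only for two other outcomes: "To test the effect of the intervention on outcomes (depressive symptoms, pain), generalized estimating equations will be used (GEE". It adds that "interpretation of the results will be based on the effect size associated with the time by group interaction for each outcome". Frailty is not mentioned in that section.

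The Outcomes section also says: "The Frail Scale will be used to measure frailty for virtual data collection visits". It lists the five topics that scale asks about, but gives no score range and no bands.

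**The concern.** Three bands are a reasonable way to decide who is eligible, but a coarse way to measure change over 12 weeks. A woman who enters at 2, 4 or 5 and loses one criterion stays in the same band. Her improvement counts only if the score itself is analysed.

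This matters because the pilot exists to produce effect sizes for a later trial; the plan says it is not powered for significance and will interpret effect sizes. An effect size on status mixes two things: what the intervention did, and how many women happened to enter just above a cut-point. A definitive trial with a different entry mix could not rely on it. If the scale is left open, it could also be chosen after the data are seen.

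**Working it through.** **Plan's own figure.** There is none for frailty. The sample size section gives only a retained number of about 25 per arm, used below for scale.

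**Step 1: which one-point moves change status.** The cut-points are from the Outcomes section and the entry range from the inclusion criteria. No assumption is needed.

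| Entry score | One point better | Status changes? | One point worse | Status changes? |
|---|---|---|---|---|
| 1 | 0 | yes | 2 | no |
| 2 | 1 | no | 3 | yes |
| 3 | 2 | yes | 4 | no |
| 4 | 3 | no | 5 | no |
| 5 | 4 | no | not possible | – |

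Hidden improvements: 3 of 5. Hidden worsenings: 3 of 4. Together: 6 of 9.

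**Step 2: share of one-point improvements hidden.** If improvement is equally likely at each entry score, the hidden share is P(2) + P(4) + P(5). The documents give no entry distribution, so these mixes (percent at scores 1/2/3/4/5) are assumptions:

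- 20/20/20/20/20: 20 + 20 + 20 = 60%
- 10/15/30/25/20: 15 + 25 + 20 = 60%
- 20/30/25/15/10: 30 + 15 + 10 = 55%
- 30/30/25/10/5: 30 + 10 + 5 = 45%
- 45/25/20/7/3: 25 + 7 + 3 = 35%
- 50/15/30/4/1: 15 + 4 + 1 = 20%

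The last mix is deliberately concentrated at 1 and 3.

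**Step 3: effect size on the count and on status.** Assumed rates: control improves by one, stays or worsens by one with probability 0.20/0.60/0.20; DAPPER 0.35/0.45/0.20. A woman at 5 cannot worsen. Bands are scored 0, 1, 2. d is the difference in mean change divided by the square root of the average of the two variances.

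Uniform entry, count:
- DAPPER mean −0.35 + 0.20 × 0.8 = −0.19; variance 0.35 + 0.16 − 0.19² = 0.4739
- Control mean −0.20 + 0.16 = −0.04; variance 0.20 + 0.16 − 0.04² = 0.3584
- d = 0.15 / √0.41615 = 0.23

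Uniform entry, status (improvement visible from 1 and 3, share 0.4; worsening visible from 2 only, share 0.2):
- DAPPER mean −0.14 + 0.04 = −0.10; variance 0.18 − 0.01 = 0.17
- Control mean −0.08 + 0.04 = −0.04; variance 0.12 − 0.0016 = 0.1184
- d = 0.06 / √0.1442 = 0.16

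The sample-size ratio for equal power is (d on count / d on status)². From unrounded values:

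| Entry mix | d, count | d, status | Ratio |
|---|---|---|---|
| 20/20/20/20/20 | 0.23 | 0.16 | 2.17 |
| 30/30/25/10/5 | 0.22 | 0.18 | 1.47 |
| 45/25/20/7/3 | 0.22 | 0.21 | 1.09 |
| 50/15/30/4/1 | 0.22 | 0.26 | 0.71 |

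In the last row status gives the larger d because it shows most improvements (80%) while hiding most worsenings.

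**Step 4: other assumed rates.** With improvement in 45% against 20% and worsening in 10% against 15%, over five mixes that exclude the last row above, d is 0.48–0.49 on the count and 0.29–0.39 on status. The relative efficiency of status is 0.36–0.65, a ratio of 1/0.65 = 1.5 to 1/0.36 = 2.8.

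Within each set of rates, d on the count barely moves with the entry mix, while d on status moves a good deal.

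**The case against.** The strongest reply is that the plan never says frailty will be analysed in bands. A reader might infer that it does, from the word status in the Abstract and the bands in the Outcomes section. That is the natural reading, but the Objectives speak only of reduction in frailty and the Analytic approach names no frailty analysis. This objection stands: the loss is conditional on status being used. It does not remove the point, since naming the scale is needed either way.

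A reader might also infer that most women who improve would be missed. Six of nine is a count of possible moves, not of women. The share of one-point improvements hidden falls below half in several of the mixes above.

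It is tempting to quote a fixed sample-size penalty, such as 1.5 to 2.2 times. The documents give no entry mix or transition rates, and the ratio drops to 1.09 and then 0.71 as entry concentrates at 1 and 3. Nor is the ratio a statement about precision: with 25 per arm the standard error of d is about √(2/25) = 0.28 on either scale, well above the gaps of about 0.04 to 0.07 in the first two rows of Step 3.

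Finally, it cannot be said that the 0–5 count is already in hand for everyone. It underlies status wherever the phenotype is measured. But women may choose virtual visits, where the Frail Scale is used with no stated scoring, and section 6b lets them decline the walking test. The same gaps would affect status.

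**Conclusion.** The point holds in conditional form. The plan makes frailty status a primary outcome, attaches only a three-band scale to it, and states no other scale or model for the frailty effect size. If status is used, 6 of 9 possible one-point moves are invisible; this follows from the protocol's own cut-points and entry range alone. About 35–60% of one-point improvements would be hidden over a range of assumed mixes, and fewer if women concentrate at scores 1 and 3.

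The efficiency gain from the count is usually material, but its size, and in some mixes its direction, depends on assumed rates. The firmer argument is stability: in these illustrations the count's effect size hardly depends on who happens to enter, and the status effect size does. That is what a pilot needs to pass on to a definitive trial.

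**What to change.** Pre-specify change in the number of frailty criteria met (0–5) from baseline to week 12 as the effect-size measure for the second specific aim, and name the model for it. Compare each woman's change only within the same instrument, phenotype with phenotype or Frail Scale with Frail Scale, and state how the Frail Scale is scored. Keep robust, pre-frail and frail for eligibility and for a descriptive table of transitions by arm.

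The cost is a short addition to the outcome definition and the analysis section. Where the phenotype is measured at both visits, no new data are needed. There are two downsides. A one-criterion change is less familiar to clinicians, which the transition table partly answers. And women whose instrument changes between visits, or who decline a component, will lack a comparable count; their number should be reported.

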### **2. Objectives**

The aims of this pilot project are to 1) test the Depression and Pain Perseverance through Empowered Recovery (DAPPER) program for feasibility and acceptability. Specifically, we will 1) test the effect size of DAPPER on pain and depressive symptoms from baseline to 12 weeks (compare intervention to wait list control group) and then at 24 weeks to compare the intervention group to wait list control group once again, 2) estimate preliminary effect sizes for DAPPER in reduction of frailty, and 3) measure effect sizes and feasibility of measuring cytokines.

This study is being supported through funding from the Harold Amos Medical Faculty Program and the Johns Hopkins Older Adults Independence Pepper Center.

### 3. Background

#### **BACKGROUND AND SIGNIFICANCE**

African American women experience higher rates of comorbid conditions and related health consequences than other racial/ethnic groups. Among the health consequences that African American women differentially face are pain, depressive symptoms, and frailty. Pain, depressive symptoms, and frailty can occur in a multi-directional cycle.

#### **Pain and Depression**

Pain and depression frequently co-occur among older adults with comorbidities and can exacerbate one another; treatment is needed to avert frailty, disability, and mortality. In older adults it can be difficult to treat both pain and depressive symptoms. Older adults are not only at high risk for side effects from pharmacological interventions but also often don't experience full relief from them; hence, it is vital that non-pharmacological mechanisms are developed to treat the pain-depression cycle among older adults.

The intersection of race, gender, and age put older minority women at an increased risk of experiencing undertreated depressive symptoms and pain that can significantly diminish their quality of life. Depressive symptoms among African Americans are more severe than other racial/ethnic groups. Although half of adults with depressive symptoms undergo treatment, only 45% of African Americans with depressive symptoms undergo treatment. African Americans experience higher rates of pain and are prescribed pain medications less often than non-Hispanic Whites. Some antidepressant medications, opioids, and NSAIDS can improve depression and decrease pain among older adults/older African Americans; however, they may experience high rates of side effects from these medications. Hence, non-pharmacological pain interventions can be combined with pharmacological interventions to help alleviate pain and depressive symptoms in older African American women.

#### **Frailty and Pain**

African American women experience higher rates of disability and frailty than non-Hispanic Whites or African American men. Among many potential mechanisms underlying this disparity, pain is a factor that is amenable to interventions. Frailty increases the perils of experiencing chronic pain; whereas, chronic pain can contribute to frailty by increasing a risk of decreased activity and gait speed. Pain has been identified as a modifiable factor that may improve frailty, if addressed. Pain management in older frail women improves quality of life.

#### **Frailty and Depression**

People with depression are at a fourfold increase of experiencing frailty. Increases in both frailty and depression are related to higher odds of nursing home admissions and higher risks for falls. Depressive symptoms may impact activity levels, energy, and nutrition, which all play a role in the etiology of frailty. Depressive symptoms may be a modifiable factor that could have an impact on frailty in older African American women.

Older African American women are crucial to target for intervention not only because of their heightened frailty prevalence, but because they are at higher risk of pain than other racial/ethnic groups and African American men. Additionally, the relationship and outcomes of pain, depressive symptoms, and frailty are exacerbated in older women.

#### **Gaps in the Literature Addressing Pain, Depressive Symptoms, and Frailty**

**Communication:** According to research, African Americans experience difficulties in communicating with their health care providers. Ghods and colleagues reported that among 109 adults with depressive symptoms, African Americans had less rapport building with their health care providers and less depressive symptom related statements than non-Hispanic White counterparts. In another study, researchers identified that among African American and non-Hispanic Whites with musculoskeletal pain that discussions about pain with their primary health care were sparse and communication about chronic pain was often challenging. Hansson and colleagues (2018) conducted focus groups with health care providers and identified that there were challenges in communication among health care providers and frail older adults. Interventions that include coaching and education strategies that target communication can be effective in improving communication between African Americans and their primary health care providers. Studies show that a communication intervention has the potential to improve patients' communication with health care providers and results in better health management.

**Non-pharmacological Strategies:** There is limited data on culturally appropriate, non-pharmacological strategies to manage depressive symptoms, pain, and frailty within older African American women. To our knowledge non-pharmacological studies targeting pain have not shown significant improvements in African Americans, or showed improvement in depression but had small numbers of African Americans in the sample.

**Self- Management Interventions:** Self-Management interventions have been successful at addressing conditions such as depression and physical function among older adults. Self-management is defined as the tasks or strategies that are conducted within the living environment that promote health by addressing conditions or symptoms across five core areas: problem solving, decision making, resource utilization, partnerships with healthcare providers, and taking action. A self-management behavioral activation intervention that has effectively treated depressive symptoms in older African Americans is the Get Busy Get Better/Beat the Blues intervention (NIMH, RO1 MH 079814, PI :[name]). Get Busy Get Better included 208 community dwelling African Americans with depressive symptoms in Philadelphia. The intervention included up to ten visits by licensed social workers over 4 months. The visits included ongoing education about depression and related treatment for depression. The participants did set their own goals (decision making) and the education and treatment (problem solving) assisted them with achieving these goals. Another intervention, the Community Aging in Place, Advancing Better Living for Elders (CAPABLE) study (NIH, R01-AG040100, PI: [name]), is a person directed tailored program in which participants set their own goals (decision making) and work with occupational therapists and nurses (partnerships with healthcare providers) to use individually tailored strategies (problem solving) to meet their self-selected goals. The participants select goals from areas related to physical function as well as pain management, depression, falls, and communication with health care providers. CAPABLE shows improvement in physical function, pain, depression, and disability outcomes. CAPABLE has been replicated in 28 sites in 14 state including statewide in Massachusetts. To our knowledge, there have been no tailored self-management person directed interventions that address a group of conditions such as pain, depressive symptoms, and frailty among older African American women.

**Development of DAPPER:** Given the need for a tailored self-management intervention targeting pain, depressive symptoms, and frailty in older African American women, the gaps in the current literature, and documentation of successful interventions, we have developed an intervention. The proposed intervention is called Depression and Pain Perseverance through Empowered Recovery (DAPPER). We are adapting the Get Busy Get Better intervention by adding components (e.g. nurse visits and person directed goals) from the CAPABLE study for this intervention. We will further develop the intervention through this pilot test. Specifically, we are using the structured visits and visit content guidelines from Get Busy Get Better. We are also using the model of nurse visits from CAPABLE in which the participants are universally assessed,

[figure not shown]
and their goals address the areas that are assessed. In DAPPER, the participants work with nurses to incorporate strategies surrounding communication with health care providers and non-pharmacological strategies that will help them meet their identified health goals surrounding pain and depressive symptoms. Through addressing these goals, we hope to impact frailty outcomes. Given the participants may have different types of pain and severity of depressive symptoms they will need individualized goals and tailored strategies to meet their goals. **The structure of the intervention, number of visits, and content of each visit remains the same across all participants. We have seen this model prove successful in the CAPABLE study.**

